Patients requiring parenteral antibiotic treatment for ABSSSI have routinely been admitted to the hospital, regardless of the degree to which they may require other hospital services such as drainage or debridement.⁹ In one recent examination of 619 adult patients presenting to 12 US EDs with SSSI, Talan et al noted that for 85% of patients admitted to the hospital ($n=94$), their doctors indicated that the reason for admission was the requirement for parenteral antibiotic therapy, and for approximately 41% of admitted patients ($n=39$), this was the only reason for admission.¹⁰ The advent of outpatient parenteral antibiotic therapy (OPAT), which has been shown to be a safe and effective means by which parenteral antibiotic treatment can be administered,¹¹ has provided an opportunity to rethink this paradigm. Current practice guidelines for the management of ABSSSI in EDs and hospitals have suggested that patients without a need for admission—defined as presence of hemodynamic instability, necrotizing fasciitis, and/or unstable comorbidities—do not require admission and instead could be managed as outpatients. Interestingly, these guidelines note that the presence of systemic signs of infection such as fever, in the absence of the aforementioned risk factors, are not cause in and of themselves for admission.³ Guidelines for the selection and management of patients receiving OPAT outline other relevant criteria, including psychosocial factors that may threaten the ability to render care on an outpatient basis.¹¹ Yet, even with recommendations for outpatient care in clinical guidelines, a lack of clear care pathways for ABSSSI patients in the ED limits use in practice. The development of new antibiotic therapies provides the opportunity to successfully design and implement a new care pathway, due to the accelerated dosing schedules and ease of administration provided by long-acting parenteral antibiotics. Long-acting parenteral antibiotics may be an important component of a care pathway in the ED for treatment of ABSSSI. Currently, there is a paucity of research that exists regarding a new clinical pathway in the ED for treatment of ABSSSI patients and the place of long-acting parenteral antibiotics in therapy.

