2.1 Overview

This study will employ a “pre-post” pragmatic design, which will consist of both a pre-period, or an observational baseline period, and a post-period, or an interventional period (Figure 1). During the pre-period, each participating site will implement the first component of the critical pathway through implementation of guideline-based criteria to identify patients at the point of care in the ED, obtain informed consent, and monitor enrolled subjects. Sites will initiate treatment for ABSSSI with “usual care,” defined as site- or physician-specific antibiotic treatment of ABSSSI with coverage for a known or suspected Gram-positive infection (e.g., vancomycin, linezolid, and daptomycin) to each study subject who meets all inclusion and exclusion criteria. Blinding of treating physician to subject enrollment in the study during the pre-period will ensure unbiased provision of usual care. During the “post” period, for all subjects who provide informed consent and are subsequently enrolled, each participating site will additionally implement the second component of the new critical pathway, use of dalbavancin, at the point of care in the ED to each study subject who meets all inclusion and exclusion criteria.

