3.1.2 Primary and secondary outcomes

[figure not shown]
Primary and secondary outcomes are presented in in Table 3. Outcomes will be assessed during initial care (the date of enrollment to 14 days) and follow-up (30 days after initial care) unless otherwise specified.

Table 3. Primary and secondary outcomes

Measure	Description
Hospital admission rate at initial episode of care	The rate of initial hospitalization for the treatment of ABSSSI
Total admitted hospital days during initial care and follow up	Includes days during the initial hospitalization (for those initially hospitalized) and all other hospitalizations
Infection-related total admitted hospital days during initial care and follow up	Includes days during the initial hospitalization (for those initially hospitalized) and all other infection-related hospitalizations
ED length of stay at initial episode of care (time from triage to release from ED)	Time spent in ED in hours from triage to release (either admitted to the hospital, admitted to observation, or released to home)
Infection-related major surgical interventions that required operating room time during initial care and follow up	Number of major unexpected surgeries
	Number of major expected surgeries
	Number of all major surgical interventions unexpected or expected
Infection-related hospitalizations during initial care and follow up	Number of infection-related hospitalizations

Measure	Description
Infection-related hospitalizations during initial care and follow-up that resulted in admission to Intensive Care Unit (ICU)	Number of infection-related hospitalizations resulting in admission to the ICU.
All cause hospitalizations in the 30 days post discharge from the hospital or release from the ED	Number of all hospitalizations for subjects discharged from the ED and re-hospitalizations for subjects who had an initial hospital admission
Infection-related ED visits during initial care and follow up	Number of unexpected visits to ED
	Number of expected visits to ED
	All visits (unexpected and expected) to ED
Infection-related outpatient healthcare visits (e.g., physicians' office visits, ED visits, infusion center visits, home health visits) during initial care and follow up	Unexpected visits, by site (e.g., physicians' office visits, ED visits, infusion center visits, home health visits)
	Expected visits, by site (e.g., physicians' office visits, ED visits, infusion center visits, home health visits)

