3.2 Data collection

Information on baseline characteristics, outcomes, and other measures will be collected following subject enrollment in the study and will be based on the medical record and CRFs that will be developed exclusively for use in this study.

Data collection will involve the use of the CRO's electronic data capture (EDC) system through use of CRFs, to which only authorized personnel will have access. Subject's data are to be entered into the EDC system by the investigator or designee using their assigned EDC user account. After data entry into the EDC system by the investigator or designee, a combination of manual and programmatic edit checks will be used to review the data for completeness, logic, and adherence to study protocol. As a result of these edits checks, data monitoring, and reviews, queries may be electronically issued to the site and should be answered electronically via the EDC system.

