6.2.6 Outcomes

6.2.6.1 Primary Outcomes

Primary Outcome: Hospital Admission Rate at Initial Episode of Care

Hospital admission at initial episode of care will include infection-related stays upon discharge from the index ED visit (derived and described in Appendix B). Tables will reflect patient counts and percentages for hospital admission (yes, no) at the initial episode of care by the pre-period and post-period for the FAS population. Summary rows will be repeated by site.

The primary analysis will consist of hypothesis testing using a one-sided, two-sample Pearson chi-square test for proportion difference with a normal approximation. An appropriate alternative method will be selected if a major violation to an assumption is present.

Because the baseline characteristics of the pre-period may differ from those of the post-period, a secondary analysis using a multivariate logistic regression analyses will be implemented. This model will assume mutual independence between the sites.

Clinically relevant baseline characteristics of interest for the adjusted analysis include the following variables: age, gender (Male, Female), race (White/Caucasian, Black or African American, Other), employment status (Full-Time, Part-Time, None), insurance plan type (Private commercial plan, Government funded, Uninsured, Other), Charlson Comorbidity Index, lesion surface area (<75cm², =>75 cm² – 150 cm², >150 cm²), infection type (Wound infection, Cellulitis/erysipelas, Abscess), prior health resource use (Yes, No, Unknown), prior antibiotic treatment failure (Yes, No, Unknown), presence of SIRS criteria (<2 or >=2), presence of recurrent infection in prior 6 months (Yes, No, Unknown), any health resource use in prior 3 months (Yes, No, Unknown), as well as is patient was immunocompromised (Yes, No, Unknown). Patients will be defined as immunocompromised if they have evidence of any of the following at baseline: Connective tissue disease, diabetes mellitus, leukemia, or malignant lymphoma. Categorical variables will be collapsed where possible. The primary predictor variable will be a pre/post-period indicator, and potentially other selected characteristics will be forced into the model based on clinical rationale and distributions observed in the

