6.2.7 Hospitalizations, Emergency Department Visits and Observational Unit Stays

The number and percent of patients who were admitted to hospital or not admitted to the hospital following their initial evaluation in the ED will be

[Redacted]

tabulated in a frequency table by the pre-period and post-period for the FAS population. Patients' care pathways, including time spent in each setting of care (ED, observation unit, initial hospitalization, and ICU), will be summarized with descriptive statistics. The number and percentage of patients will be reported for treatment with dalbavancin, alive or dead at discharge, and discharge disposition location. All of the aforementioned variables will be reflected in listings.

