6.2.9 Antibiotic Treatments and Concomitant Medications

Concomitant medications taken three months prior to study start will be coded using the WHODRUG dictionary, Version B2 201609 or later, and the number and percentage of patients will be summarized in tables. Antibiotic usage during the study will also be coded using the WHODRUG dictionary, Version B2 201609 or later, and summarized in tables. The most current WHODRUG

dictionary will be used at the time of analysis. These prior non-antibiotic medications used for chronic conditions will be reported in listings, including the medication name (coded), reason for prescription, route, and start date and end date. All medications will be summarized using descriptive statistics by the pre-period and post-period for the FAS population. For post-period patients, discharge to complete care in an outpatient setting on the same day Dalvance was provided and reasons for not being discharged to an outpatient setting will be summarized by patient counts and percentages.

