Appendix B: Derived Variables

Analysis Section (Visit)	Variable (Units)	Definition
General (Baseline)	Enrollment date	Informed consent date
General (Baseline)	Baseline date	Initial ED admission date
General (Initial Care)	Initial care indicator	If enrollment date \leq date \leq enrollment date + 13 days then = Yes Else = No
General (Follow-up)	Follow-up indicator	If enrollment date + 14 \leq date \leq enrollment date + 43 days then = Yes Else = No
Demographics (Baseline)	Age (years)	Round down to nearest integer((Initial ED admission date - date of birth + 1)/365.25), when both dates are available.
Demographics (Baseline)	BMI	weight (kg)/ [height(m)] ² Where necessary, height and weight will be converted to proper units.
Infection Characteristics (Baseline)	CCI	Will be scored as described in Appendix C. Includes variables for raw score and 10 year survival probability.
Infection Characteristics (Baseline)	Fever	If temperature > 38 ° C then =Yes Else =No
Infection Characteristics (Baseline)	Morbid Obesity	If baseline BMI \geq 40 then =Yes Else =No
Infection Characteristics (Baseline)	SIRS Criteria Met	SIRS criteria include abnormalities in temperature, heart rate, respiration, and white blood cell count. Specifically included are: 
 Fever of more than > 38.0°C or hypothermia with temperature < 36.0°C

[figure not shown]
[figure not shown]
Analysis Section (Visit)	Variable (Units)	Definition
		
 • Tachycardia with heart rate > 90 beats/minute or • Tachypnea with respiratory rate of > 20 breaths/minute or PaCO₂ of less than 32mmHg • Abnormal white blood cell count: leukocytosis >12,000/microliter, leucopenia <4,000/microliter, or >10% immature cells (bands).^{3,4} 
If 2 or more criteria present = Yes Else = No

Antibiotic Medications (Initial Care and Follow-up)	Days Received Antibiotic Medication	
Σ (Medication end date – Medication start date +1), when both dates are available. If dates overlap (e.g., end date and next start date are identical) then subtract 1 from summation for each occurrence.

Primary Outcome	Hospital Admission At Initial Episode of Care	
If discharge destination from the initial episode of care = Hospital and the reported hospitalization where discharge date = hospital date is infection-related then = Yes, Else = No

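### The primary outcome counts an index admission only if it is recorded as infection-related; the label is undefined, is not assigned blind to period, and has no pre-specified any-reason check.

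*SAP*

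**What the plan says.** The primary objective in both documents (Protocol 1.3, SAP 2.1) is the difference in hospital admission rate at the initial episode of care, with no restriction by reason. The definitions are narrower:

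- Protocol Table 3 (section 3.1.2) describes the outcome as "The rate of initial hospitalization for the treatment of ABSSSI" and gives no rule for deciding it.
- SAP 6.2.6.1: "Hospital admission at initial episode of care will include infection-related stays upon discharge from the index ED visit".
- SAP Appendix B requires that the discharge destination is the hospital and that "the reported hospitalization where discharge date = hospital date is infection-related then = Yes". All other cases are scored No.

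On who applies the label, Protocol 3.2 says only: "Subject's data are to be entered into the EDC system by the investigator or designee using their assigned EDC user account". The blinding described in Protocol 2.1 concerns the treating physician in the pre-period: "Blinding of treating physician to subject enrollment in the study during the pre-period will ensure unbiased provision of usual care". No blinding is described for the post-period or for classifying outcomes.

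SAP 6.1.1 admits a post-period patient to the full analysis set only after a dose of dalbavancin. Protocol 2.1 places that treatment in the ED, and Protocol 2.2.2 describes a single-dose regimen.

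SAP 6.2.7 tabulates the unfiltered count by period: "The number and percent of patients who were admitted to hospital or not admitted to the hospital following their initial evaluation in the ED". That table is descriptive. It is not tested or named as a check on the primary result.

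**The concern.** Every enrolled patient comes to the ED with a skin infection, so whether the patient then went to an inpatient bed is close to a matter of record. Whether the stay was infection-related takes judgement.

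The circumstances of that judgement differ by period. In the pre-period, an admitted patient may still have most of an antibiotic course ahead. In the post-period, the planned regimen has already been given in the ED, and what keeps the patient in hospital may be a comorbidity or a social need. Under the Protocol Table 3 wording in particular, the same kind of stay could be counted in one period and not in the other. That would lower the post-period rate without any fewer patients being admitted.

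This outcome carries the only confirmatory test, because SAP 6.2 makes all secondary testing exploratory. A fall in the recorded rate would naturally be read as a fall in admissions.

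**Working it through.** **Inputs.** Rates 38% and 23%, one-sided α = 0.05, at least 80% power, 161 per period (Protocol 5.3, SAP 6.1.2); one-sided Pearson chi-square test with normal approximation (SAP 6.2.6.1); original attrition assumption 10% (SAP 5.0). The share *f* of post-period admissions recorded as not infection-related is **not in the documents**. It is an assumption, shown over a range.

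**1. The plan's own figure.** With p̄ = (0.38 + 0.23)/2 = 0.305:

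n = [1.645·√(2p̄(1−p̄)) + 0.842·√(0.38·0.62 + 0.23·0.77)]² / 0.15² = 115.4, so 116 per period.

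Power is 90.2% with 161 per period, and 87.4% with 145 (161 × 0.9 = 144.9). The statement of at least 80% power is correct, and nothing here disputes the sample size.

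**2. Effect of differential labelling when there is no true effect.** Let 38% of patients be admitted in both periods, with every pre-period admission counted. The recorded post-period rate is p₂ = 0.38(1−f). The chance of a significant result is

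Φ{[(0.38 − p₂) − 1.645·SE₀]/SE₁},

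with SE₀ = √(2p̄(1−p̄)/n), SE₁ = √([0.38·0.62 + p₂(1−p₂)]/n) and p̄ = (0.38 + p₂)/2.

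Example, f = 10%, n = 161: p₂ = 0.342, SE₀ = 0.0535, SE₁ = 0.0535, giving Φ(−0.936) = 17.5%.

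| f (assumed) | Recorded post rate | Rejection, n = 161 | Rejection, n = 145 |
|---|---|---|---|
| 0% | 38.0% | 5.0% | 5.0% |
| 5% | 36.1% | 9.8% | 9.5% |
| 10% | 34.2% | 17.5% | 16.6% |
| 15% | 32.3% | 28.3% | 26.5% |
| 20% | 30.4% | 41.8% | 38.9% |
| 30% | 26.6% | 70.8% | 66.8% |

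**3. In patients.** 38% of 161 is 61.
- With 61 truly admitted in each period, relabelling 14 post-period stays (23%) gives 61 v 47 and z = 1.65, just past the critical value of 1.645. Relabelling 13 gives 61 v 48 and z = 1.53, which is not significant.
- At the planned result (61 v 37), restoring 11 excluded post-period stays also gives 61 v 48, and significance is lost.
- Producing the whole 15-point difference by labelling alone would need 15/38 = 39% of post-period admissions relabelled.

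**4. A ceiling, not a rate.** Protocol 1.1.3 cites an ED study in which, for 85% of admitted patients, physicians indicated that "the reason for admission was the requirement for parenteral antibiotic therapy"; for about 41% it was the only reason. So 85 − 41 = 44% had another reason as well, and 0.44 × 38% = 16.7 percentage points. This is an upper limit on mixed-reason admissions, since second reasons such as drainage or debridement are themselves infection-related. It does not show how many stays would be relabelled.

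**5. Power of the any-reason version.** If 23% is the infection-related post-period rate and 10% of post-period admissions are unrelated, the any-reason rate is 0.23/0.9 = 25.6%. Against 38%, with no unrelated stays in the pre-period, power at 161 per period is 77.6%; with 20% unrelated (28.7%), it is 54.6%. If the same 2.6 points of unrelated stays occur in both periods (40.6% v 25.6%), power is 89.1%.

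**The case against.** The SAP restriction follows Protocol Table 3, so it is a legitimate choice of outcome. The condition is that the stay is infection-related, not that the patient needs further intravenous antibiotics. A patient with a large lesion dosed hours before still has an active infection, and admission for monitoring or drainage would naturally keep the label. SAP 6.2.7 shows the unfiltered count by period, SAP 6.2.5.2 shows all-cause hospital days, and Protocol 5.4 provides source-document review by the contract research organization. A large gap between any-reason and infection-related admissions would be visible. Parts of both documents are redacted or not shown and the case report form is not supplied, so a definition may exist there.

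Most of this stands, and it limits what can be said. A reader might infer that the label changes meaning once dalbavancin has been given; no passage says so. A reader might also infer that an unblinded site assigns the label throughout. Site assignment is suggested by investigator data entry but not stated, and the treating physician is blinded to enrollment in the pre-period. Nor does the post-period summary in SAP 6.2.9, where "reasons for not being discharged to an outpatient setting will be summarized by patient counts and percentages", show bias: it addresses a question specific to that period and is not said to feed the label.

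What the objection does not supply is a rule tying the unfiltered count to the primary conclusion. A descriptive table with no stated role leaves the interpretation of any divergence to be settled after the data are seen.

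**Conclusion.** The point holds as a vulnerability in the definition, not as demonstrated bias. An ED-to-inpatient transfer can be scored as not admitted on a label that the available text neither defines nor protects from knowledge of period. The likely direction of any differential use favours the pathway.

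The size depends on an assumed relabelling share. A share of 5% roughly doubles the one-sided error, to about 10%; 10% gives about 17% and 20% about 42%. These figures assume 38% truly admitted in both periods, 161 patients per period and no exclusions in the pre-period. If pre-period stays were excluded at a similar rate, most of the distortion would disappear. The documents do not support a claim that the planned 15-point effect is an artefact.

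A smaller related point: the Appendix B rule also scores an unmatched date or a missing label as not admitted, which sits badly with the observed-case approach in SAP 6.1.5.

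**What to change.** In SAP 6.2.6.1 and Appendix B:

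1. Keep the current primary outcome.
2. Pre-specify admission to an inpatient bed from the index ED visit for any reason as a named sensitivity analysis, with the same one-sided test and the same adjusted model.
3. State one definition of infection-related that applies to both periods.
4. Show both versions in Table 10, with the number of index admissions in each period excluded as not infection-related.
5. State that, if the two versions diverge, the conclusion is limited to infection-related admissions and the divergence is reported.

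The cost is SAP wording and a few rows in Table 10; the unfiltered count is already planned under SAP 6.2.7, and the primary test and its α are unchanged. The drawback is dilution by unrelated admissions: in the 10% example, power for the any-reason version is about 78%, against 90% for the primary outcome. Failure of the sensitivity analysis to reach significance should therefore not by itself overturn the primary result; the two estimates and the exclusion counts should be read together.

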4.10 Potential Hy's Law cases

Every subject that meets potential Hy's law criteria,

- ALT or AST $\geq 3 \times \text{ULN}$ AND
- Total Bilirubin $\geq 2 \times \text{ULN}$ AND
- Alkaline Phosphatase $< 2 \times \text{ULN}$

occurring anytime from the time he or she signs the ICF for the trial until the final follow up visit, investigators will notify the sponsor immediately when all the above criteria have been met. A potential Hy's law case will be sent directly to the sponsor by emailing [contact] on an AE of Special Interest Form along with the SAE Report Form as soon as possible (within 24 hours of learning of the potential Hy's law). The CRF for potential Hy's law cases will be completed within seven calendar days. Every effort to determine the cause of the liver enzyme abnormalities will be made, and close monitoring will be initiated in conjunction with the medical monitor and in accordance with the FDA "Guidance for Industry: Drug Induced Liver Injury- Pre-Marketing Clinical Evaluation" July 2009.

5 Data analysis

Frequency and proportion of subjects deemed eligible and ineligible for study enrollment based on each of the inclusion/exclusion criteria will be summarized. The frequency and proportion of subjects who successfully complete the study, withdraw, were lost-to-follow-up, and who terminated the study early, will also be reported. Subject characteristics at baseline will be summarized and described for all enrolled subjects and compared between the pre- and post-periods. Site characteristics will also be described. Descriptive statistics (count, mean, standard deviation, range for quantitative variables, and counts and percentages for categorical variables) will be reported for all outcomes. The difference in study outcomes between the pre- and post-period will be assessed using appropriate statistical methods, accounting for study site, with adequate power. The primary outcome will be tested for simple superiority, and subsequently, tested for non-inferiority with a 10% margin between the pre- and post-periods.

All analyses will be specified in a detailed statistical analysis plan (SAP) that will be prepared subsequently and before database lock. The SAP will include table and figure shells.

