5.0 Changes in the Protocol Specified Analyses

Infection characteristics described in the protocol including hyperglycemia (>120mg/dL blood glucose or site-specific definition), thrombocytopenia (<150,000 platelet count or site-specific definition), acidosis (<7.35 pH of the blood or site-specific definition or described in medical chart), hyponatremia (<135 mEq/L blood sodium or site-specific definition), uremia (as described in medical chart), and anemia (14-18 g/dL hemoglobin for men or 12-16 g/dL hemoglobin for women or site-specific definition) will not be derived from laboratory values or reported in analysis.

An interim analysis was performed after the enrollment of approximately 75 patients to evaluate the original sample size. It was determined a sample size greater than 322 would be needed for hypothesis testing of the primary outcome of total number of days spent in the hospital. Factors that contributed to the large sample size include:

- The observed variation was larger than the original estimate (SD = 3.0 days).
- The observed attrition rate was larger than the original assumption (10%).

Additionally, the observed mean total LOS was much smaller than the protocol assumption (4.0 days). It was determined that observing a statistically significant reduction in the total number of days spent in the hospital in the post-period was unlikely.

Based on results of the interim analysis, an adjustment was made at the time of the analysis to revise the primary outcome from total admitted hospital days to hospital admission rate at initial episode of care. The initially estimated final enrollment of 322 subjects, including adjustments for attrition, would support one-sided hypothesis testing (two-sample Pearson chi-square test for proportion difference with equal group weights using a normal approximation) with a significance level of 0.05 and at least 80% power assuming hospital admission rate comparing the pre- and post-periods were 38% versus 23%. This change has been reflected in the protocol, Amendment Version 3.0.

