6.1 General Considerations

6.1.1 Analysis populations

Enrolled Set

The enrolled set consists of all patients who have signed informed consent and met all study eligibility criteria. Data will be summarized on disposition and baseline characteristics. Output will be summarized by study period (pre-period vs. post-period). All data listings will be reported for the enrolled set unless specified in Section 5.2.

Full Analysis Set

The full analysis set (FAS) population consists of all enrolled patients. Additionally, patients in the pre-period must receive at least one dose of antibiotics and patients in the post-period must receive at least one dose of dalbavancin for inclusion. All patients in the pre-period and post-period will be analysed. Data will be summarized by study period.

Data from all patients will be aggregated across sites, and all analyses related to protocol outcomes and baseline characteristics will be undertaken on the aggregate pre- and post-periods.

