6.1.7 Subgroup analyses

Currently no subgroup analyses are planned for this study. If applicable, analyses will be repeated for subgroups of interest. Exploratory analyses will be performed such that selected outputs are repeated by sites if needed.

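### The protocol commits to accounting for study site, but the SAP's primary test pools sites, its logistic model names no site term, and SAP 5.0 does not record the departure

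*SAP*

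**What the plan says.** **Protocol.** Section 5 (Data analysis) states that pre/post differences in outcomes will be "assessed using appropriate statistical methods, accounting for study site, with adequate power" and leaves the detail to the SAP. Section 5.3 then states power for the revised primary outcome using a two-sample Pearson chi-square test with no site stratification. Section 2.1.2 argues that the design removes site-level confounding because each site contributes patients to both periods.

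**SAP.** Section 6.2.6.1: "The primary analysis will consist of hypothesis testing using a one-sided, two-sample Pearson chi-square test for proportion difference with a normal approximation". Section 6.1.1 adds that "all analyses related to protocol outcomes and baseline characteristics will be undertaken on the aggregate pre- and post-periods". For the primary outcome, site appears in these places:

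- As description: "Summary rows will be repeated by site" (6.2.6.1), and exploratory work in which "selected outputs are repeated by sites if needed" (6.1.7).
- In a sentence saying that the logistic model treats the sites as mutually independent. This names no site term.
- Not in the list of covariates for that model. Further characteristics may be forced in once imbalance is seen, but the SAP does not commit to site.

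SAP 5.0, headed "Changes in the Protocol Specified Analyses", covers laboratory-derived infection characteristics, the interim analysis and the change of primary outcome. It repeats the Pearson test there and says nothing about site.

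**The concern.** This is a non-randomised before/after comparison. Having every site in both periods protects a pooled comparison only if the mix of sites is similar in the two periods, or if mix differences are unrelated to admission rates. Nothing in the reviewed text fixes the mix. SAP 3.0 expects each site to move to the post-period at 50 patients and does not expect sites to move together, while only 161 patients are needed per period. Protocol 2.2.1 expects usual care to vary by site or physician. That sentence concerns antibiotic choice, but it makes differing site admission rates plausible.

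If high-admission sites are over-represented in the pre-period, part of the pooled drop is site mix, not pathway. If they are over-represented in the post-period, a real drop is partly hidden. By-site rows would reveal such a shift but would not correct the test.

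**Working it through.** **1. Reproduce the plan's power figure** (Protocol 5.3, SAP 6.1.2: 38% versus 23%, one-sided 0.05, 161 per period).

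Pooled rate (0.38 + 0.23)/2 = 0.305. Null SE = √(2 × 0.305 × 0.695/161) = 0.0513. Alternative SE = √((0.38 × 0.62 + 0.23 × 0.77)/161) = 0.0506. Power = Φ[(0.15 − 1.645 × 0.0513)/0.0506] = Φ(1.30) = 90%. It is 87% with 145 analysed per period and 84% with 129. Power of 80% needs 116 per period, so the plan's figure of at least 80% holds.

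**2. Bias of the pooled difference.** With site shares w and site admission rates r, and no pathway effect:

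bias = Σ (w_pre − w_post) × r

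This is zero if shares match, if rates match, or if share differences are unrelated to rates. Unequal shares alone are not enough.

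**3. Assumed mix shift.** Two site types averaging 38%, null SE = √(2 × 0.38 × 0.62/161) = 0.0541, type I error = 1 − Φ(1.645 − bias/0.0541):

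| Site rates | Mix shift | Bias | Formula | Simulated, pooled | Simulated, stratified |
|---|---|---|---|---|---|
| 43% / 33% | 10 points | 1 point | 7% | 7% | 5% |
| 43% / 33% | 20 points | 2 points | 10% | 10% | 5% |
| 48% / 28% | 10 points | 2 points | 10% | 10% | 5% |
| 48% / 28% | 20 points | 4 points | 18% | 18% | 5% |

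With the 20-point shift reversed at 48%/28%, a true 15-point drop appears as 11 points. Pooled power is 69%, against 91% stratified.

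**4. A less contrived mechanism.** Eight sites, lognormal recruitment rates that persist across periods, each site switching at 50 patients or when the pre-period fills, no true effect:

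| Recruitment log-SD | Pooled error, site-rate SD 5 / 10 / 15 points | Stratified |
|---|---|---|
| 0.3 | 5.0 / 5.2 / 5.0% | about 5% |
| 0.6 | 5.1 / 5.1 / 5.3% | about 5% |
| 1.0 | 5.3 / 6.8 / 8.1% | about 5% |

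Repeat runs put the last row at about 5–9%.

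**5. Power cost of stratifying.** Information is Σ n_pre × n_post/(n_pre + n_post). With equal site shares this is 161/2 = 80.5, and power is 90% pooled and 90% stratified.

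The adverse layout has three sites giving 50 each to the pre-period and five sharing the other 11 (3, 2, 2, 2, 2), against 20.1 per site post. It gives 3 × 14.35 + 2.61 + 4 × 1.82 = 52.9. That is 66% of 80.5, or about 106 per period, and power is 77% by formula and by simulation. With 145 or 129 analysed per period it is 73% or 68%.

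Stratified power drops below about 80% when information falls under 116/161 = 72%. That happened in 0%, 0.1% and 6% of simulated layouts at log-SD 0.3, 0.6 and 1.0.

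**The case against.** The strongest reply is that the SAP follows the protocol. Protocol section 5 gives one general sentence that names no stratified method, while section 5.3 names the Pearson test for this outcome, and SAP 5.0 restates that test openly. This stands in part. A reader might infer that the SAP alone overrode a clear protocol analysis and concealed it. The documents do not support that: the conflict also lies inside the protocol, and the test itself is disclosed. What is missing is any statement that site is not accounted for, and why.

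Second, a reader might infer that the pooled test is biased whenever site shares differ, or because sites switch at different times. Step 2 shows otherwise: the share differences must line up with admission rates. Staggered switching does not by itself determine the shares.

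Third, the larger errors come from invented layouts. If site weights are assumed to reverse between periods in line with admission rates, simulated pooled error can reach 77%, but nothing in the documents suggests such a layout. With modest recruitment variation the error stays near 5%.

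Fourth, the SAP allows that "An appropriate alternative method will be selected if a major violation to an assumption is present", and the table shells are a separate file not reviewed here. The clause needs a major violation and does not mention site. The shells might show how site enters the logistic model, but the reviewed SAP text does not.

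Finally, stratification can cost power and site terms load the model. Both are true and are priced under the fix.

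**Conclusion.** The inconsistency is certain on the text: Protocol section 5 commits to site, while Protocol 5.3 and SAP 6.2.6.1 use a test without it, and SAP 5.0 does not record the gap. The protocol's claim to have removed site-level confounding is not guaranteed for a pooled test.

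The bias is conditional. It rests on assumed site rates and mix, because the documents give neither, so the error rates above illustrate sensitivity and do not estimate this trial's error. The power statement is not wrong. Protocol section 5 also does not require a Cochran-Mantel-Haenszel test as such; a prespecified model containing site would meet it too. The protocol's non-inferiority step is a separate matter and forms no part of this point. It should be fixed before database lock because the remedy is cheap and uses data already held.

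**What to change.** - Reconcile Protocol sections 5 and 5.3 with SAP 6.2.6.1 by prespecifying a site-stratified analysis of the primary outcome: a Cochran-Mantel-Haenszel test with a Mantel-Haenszel risk difference and confidence interval. Preferably make it primary and keep the pooled Pearson test as a sensitivity analysis.
- Before database lock, check site-by-period counts without outcome data, and state in advance how sparse or one-period sites are combined.
- If the pooled test stays primary, record the departure from Protocol section 5 and its reason in SAP 5.0, and prespecify the site-stratified analysis as a sensitivity analysis.
- Clarify what independence between sites means for the logistic model, and state whether site enters it.

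**Cost.** SAP wording and a standard procedure. There is almost no power loss when site shares are similar (90% versus 90% at 161 per period). Power falls to about 77% if three sites supply 150 of the 161 pre-period patients, which is why the count check comes first. Seven site terms (eight sites) would add load to a logistic model with about (0.38 + 0.23) × 161 = 98 expected admissions, so that choice should be made deliberately.
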